18.0 Provisions to Monitor the Data to Ensure the Safety of Subjects*

N/A

19.0 Provisions to Protect the Privacy Interests of Subjects

PROTOCOL TITLE: A Randomized Controlled Trial of an Exposure-Based Intervention for Perfectionism

- 19.1 To protect subjects' privacy interests, all study information will only be available for members of the research team. All data will be identified by using an ID number and not subjects' names.
- 19.2 To make sure that subjects feel at ease with the research situation we will encourage them to ask questions both during the consent process and afterward. We will tell subjects that they are free to refuse to answer any question without penalty. We will explain the risks of the study and inform them in advance that the intervention may be uncomfortable, but that they are able to stop it at any time.

20.0 Compensation for Research-Related Injury

N/A

21.0 Economic Burden to Subjects

- 21.1 Subjects will not be responsible for any research-related costs.

22.0 Consent Process

- 22.1 We will be obtaining written informed consent:

- The consent process will take place online via Qualtrics.
- Subjects will be given contact information for study personnel in order to ask questions about the study before clicking that they consent to participating. Participants will be reassured that they are able to discontinue the study at any time without penalty.
- We will be following SOP: Informed Consent Process for Research (HRP-090).
- Participants will be presented with a screen in which they can choose to download a copy of the consent form after signing it.

Non-English-Speaking Subjects

N/A

Waiver or Alteration of Consent Process (consent will not be obtained, required information will not be disclosed, or the research involves deception)

N/A

Subjects who are not yet adults (infants, children, teenagers)

N/A

Impaired Adults

N/A

Adults Unable to Consent

N/A

Adults Unable to Consent

PROTOCOL TITLE: A Randomized Controlled Trial of an Exposure-Based Intervention for Perfectionism

N/A

23.0 Process to Document Consent in Writing

23.1 We will be following SOP: Written Documentation of Consent (HRP-091). Consent forms can be downloaded from Qualtrics after completion and will be kept on the encrypted [name] lab drive.

24.0 Setting

24.1 All baseline questionnaires and procedures, intervention sessions, post-test questionnaires, and follow-up questionnaires will take place outside of the lab online via Qualtrics.

25.0 Resources Available

25.1

- A power analysis based on multiple regression was conducted. The results of this power analysis gave a total sample size of 68 subjects (34 subjects per group). We will recruit up to 80 participants to account for potential drop-out.
- The time devoted to this study will last about 1.5 years.
- Baseline, post-test, and follow-up assessments will take place online via Qualtrics.
- The study team will be thoroughly trained by the investigator before the study begins. We will meet with them individually and review the protocol and consent form. We will provide them with a checklist detailing the steps involved in the study.

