1.0 Study Summary

Study Title	A Randomized Controlled Trial of an Exposure-Based Intervention for Perfectionism
Study Design	Randomized Intervention Trial
Primary Objective	Evaluate the efficacy of an exposure-based intervention for perfectionism.
Secondary Objective(s)	Evaluate the effect of the intervention on depressive, anxiety, and eating disorder symptoms.
Research Intervention(s)	Exposure-Based Intervention for Perfectionism (see details below)
Study Population	FSU student subject pool participants and community participants
Sample Size	84
Study Duration for individual participants	6 weeks
Study Specific Abbreviations/ Definitions	Exposure-based intervention for perfectionism (ETP)

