6.0 Procedures Involved*

6.1 The study will be a randomized control design, with 50% of participants receiving the ETP and 50% of subjects receiving the stress management condition.

- The stress management condition will consist of psychoeducational videos about exercise, diet, hygiene, social support, and sleep. This will be followed by relaxing videos of the rainforest, wildlife, or space. This condition is based on previous studies run by our lab, including [name] et al. (2017).

6.2 Participants will be identified using the mass screening survey distributed to the pool of psychology students maintained by the psychology department (SONA) or using a brief, 3 question screener that includes three questions from the FMPS-CM. Participants who score a 9 or higher on the screener will be invited to participate in the current study and be provided with the study passcode to sign up if they are interested.

Once they sign up, all participants will be emailed a link to the informed consent form, which will be administered using a Qualtrics survey. All participants must first complete the informed consent before beginning other study procedures. After consenting, the participant will be directed to complete the FMPS and questions to assess exclusion criteria. If the participant scores a 28 or lower on the FMPS-CM or do not meet all inclusion, they will be given credit for their time (.5 credits) and the experiment will end.

In addition to student participants recruited via the mass screener and SONA, participants from the community will be provided the opportunity to participate for monetary compensation in the form of Amazon gift cards, which will be sent to them via email. Community participants will be given a link to the informed consent form before beginning study procedures. After consenting, community participants will be directed to complete the FMPS and questions to assess exclusion criteria. If they score lower than 29 on the FMPS-CM or meet any

PROTOCOL TITLE: A Randomized Controlled Trial of an Exposure-Based Intervention for Perfectionism

exclusionary criteria, they will be told they do not qualify for the study and will not be compensated.

If participants meet inclusion criteria, they will be randomized to either the exposure-based perfectionism intervention (ETP) group or the stress management group. Based on that randomization, they will be sent one of two Qualtrics links:

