12.0 Local Number of Subjects

- 12.1* 84 subjects will be recruited, with 42 in the ETP group and 42 in the stress management group.

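### The recruitment total is 84 (42 per arm) in sections 1.0 and 12.1 but at most 80, drop-out included, in section 25.1

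*Combined protocol and SAP*

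**What the plan says.** Three places give the size of the trial.

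- Section 1.0 (Study Summary): "Sample Size 84".
- Section 12.1 (Local Number of Subjects): "84 subjects will be recruited, with 42 in the ETP group and 42 in the stress management group".
- Section 25.1 (Resources Available): "We will recruit up to 80 participants to account for potential drop-out". The sentence before it gives the power-analysis result as 68 in total, 34 per group.

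Two further statements bear on how these can be read. Section 6.1 fixes equal allocation, "with 50% of participants receiving the ETP and 50% of subjects receiving the stress management condition". Section 6.2 places consent and eligibility screening ahead of allocation: "If participants meet inclusion criteria, they will be randomized".

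No drop-out rate is given. Of the power analysis, section 25.1 says only that "A power analysis based on multiple regression was conducted". It does not report alpha, power, effect size or the number of predictors.

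**The concern.** Section 25.1 sets a maximum, and that maximum already contains the drop-out allowance. Section 12.1 commits to a number above it. Staff who recruit to 12.1 break the ceiling in 25.1; staff who stop at the ceiling fall short of 12.1.

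The number that carries the per-arm split (84) is also not the number tied to the power analysis (68 raised to 80). A reader therefore cannot tell what loss the design was meant to absorb, or whether the trial met its target once it closes at 80, 84 or something between.

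**Working it through.** **1. Do the stated totals agree?** Inputs: 84 (1.0), 42 + 42 (12.1), ceiling 80 (25.1), equal allocation (6.1).

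- 42 + 42 = 84, so 1.0 and 12.1 agree.
- 84 − 80 = 4, which is 4/80 = 5.0% of the ceiling.
- Per arm: 84/2 = 42 against 80/2 = 40, a difference of 2.

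**2. Could one number be consented and the other randomised?** Sections 12.1 and 25.1 both speak of recruiting. Section 12.1 puts all 84 into groups, so 84 is a randomised count. Consent and screening come before randomisation (6.2), so a recruited count cannot be smaller than the randomised count. A ceiling of 80 recruited cannot yield 84 in groups.

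**3. Can the totals be traced to 68?** Implied drop-out = 1 − 68/N.

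- N = 80: buffer 80 − 68 = 12 (6 per arm); 12/80 = 15.0%. In reverse, 68/(1 − 0.15) = 80.
- N = 84: buffer 84 − 68 = 16 (8 per arm); 16/84 = 19.0%. In reverse, 68/(1 − 0.19) = 83.95, rounded up to 84.

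Either total is compatible with 68 under a different unstated rate, so the arithmetic does not show which was intended. The 68 cannot be verified either, because its inputs are not reported. If one assumes alpha .05, power .80 and f² = .15, the multiple-regression calculation gives 68 with two tested predictors and 55 with one.

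**4. Where does the difference matter?** Number retained = N × (1 − loss), against the 68 required:

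| Loss | From 80 | From 84 |
|---|---|---|
| 10% | 72.0 | 75.6 |
| 15% | 68.0 | 71.4 |
| 20% | 64.0 | 67.2 |
| 25% | 60.0 | 63.0 |

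Up to 15.0% loss, both totals keep 68. Between 15.0% and 19.0%, only 84 does. Above 19.0%, neither does.

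**5. What is the difference worth in power?** The protocol gives no design effect, so these inputs are assumptions: two-sided alpha .05; a one-degree-of-freedom group test adjusted for baseline; R² change of .09 (the value section 17.1 labels medium, used here only as an illustration); baseline-outcome correlation r of 0, .4 or .5. Then f² = .09/(1 − r² − .09), the noncentrality is f² × N, and the test is F on (1, N − 3) degrees of freedom. With 15% loss, the 71.4 retained from 84 is taken as 71.

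| r | f² | No loss: 80 v 84 | 15% loss: 68 v 71 |
|---|---|---|---|
| 0 | .099 | .793 v .813 | .724 v .743 |
| .4 | .120 | .864 v .880 | .804 v .821 |
| .5 | .136 | .903 v .917 | .851 v .866 |

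The largest gap is .813 − .793 = .020, or 2 percentage points.

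**The case against.** The best case for leaving this alone is its weight. Two of the three places agree on 84, and the section devoted to participant numbers gives both the total and the split. The outlier is one clause in a section on resources and may simply be a line that was not updated. Both totals clear 68, and the difference is 2 per arm. No sum in the protocol is wrong: 42 + 42 = 84 and 34 + 34 = 68. This is therefore an inconsistency rather than a miscalculation.

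The illustrations can also be challenged. The power figures rest on inputs the protocol does not supply. The retention figures count completers only, whereas section 17.1 plans an intent-to-treat analysis with multiple imputation and section 14.2 asks those who withdraw to complete the post-test. Fewer than 68 completers is thus not the same as fewer than 68 analysed.

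Most of this stands as a limit on importance. It does not remove the contradiction. That 80 is a stale line is a guess the protocol does not support, and section 25.1 is the only place where recruitment is linked to the power analysis. The heading of section 12.0 refers to a local number, but section 1.0 gives the same 84 for the whole study, and a local count could not exceed a study ceiling anyway. The completer-based comparison is the one section 25.1 itself invites, since it presents the margin above 68 as cover for drop-out.

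**Conclusion.** The concern holds. The protocol states 84 and a maximum of 80 for the same quantity, and no reading of its text makes both true. This conclusion needs no assumption. The size is 4 participants (2 per arm), with implied drop-out allowances of 15.0% and 19.0%.

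The consequence is modest. Both totals exceed 68, no bias arises, and the power gap is about 2 points or less under the assumptions listed in the working. The retention and power figures are illustrations only. The protocol does not settle which total was intended. It should still be corrected, because the sample size is a figure the trial relies on and the correction is cheap.

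**What to change.** The sponsor should confirm one recruitment total and use it in all three places.

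- If 84 is kept: correct the ceiling in 25.1 to 84. Sections 1.0 and 12.1 stand.
- If 80 is kept: correct 1.0 to 80 and 12.1 to 80, with 40 per arm.

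As a secondary reporting point, section 25.1 should state the drop-out rate actually assumed and its basis. The total should follow from that rate; a rate of 15% or 19% should not be worked back from a total already chosen.

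The cost is protocol wording, plus the same change in any other IRB document that carries the enrolment number. Keeping 84 allows at most 4 more participants (2 per arm) than the present ceiling; keeping 80 adds none.
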